1.6 DEFINITIONS AND CONVENTIONS FOR DATA HANDLING

1.6.1 Baseline Definition

Baseline: for evaluations collected at multiple time points prior to initiation of study drug, the last assessment before the randomization day (Day 1), will be considered the "baseline" evaluation for analysis.

1.6.2 Study Day

Study Day will be calculated relative to the day of first dose (defined as Day 1), and will be used to show start/stop day of assessments and events.

Confidential Page 16 of 40

If the assessment (or event) date falls on or after the date of first dose then Study Day = Assessment Date - Date of First Dose + 1

If assessment date falls before the date of first dose then Study Day = Assessment Date - Date of First Dose

In the case of adverse events or concomitant medications where the assessment date is partially or completely missing, Study Day and any corresponding durations will follow the conventions given in Appendix 6.1.

1.6.3 End of Study

The definition of end of study is the final study visit (24 months corrected age follow-up visit).

1.6.4 Analysis Visit Windows for Follow-up Visits

For follow-up endpoints at 3, 12 and 24 months, the variables will be summarized based on the closest scheduled visit for that variable based on "analysis-defined visit windows." These visit windows have been constructed so that every observation collected can be allocated to a unique visit. No visit windows will be defined for the screening visit.

The analysis-defined visit windows for assessments conducted at 3-month, 12-month, and 24-month are summarized in Table 2.

Table 2: Analysis - Defin	ned Visit windows f	for measurements rec	orded for follow-ur	o visits

Follow-up Visit	Scheduled Study Day	Maximum Windows
3-month	3-month corrected age	Day after the discharge until
		7.5-month of corrected age
12-month	12-month corrected age	7.5-month + 1 day until 18-
		month of corrected age
24 -month	24-month corrected age	18-month + 1 day until 30-
	_	month corrected age

Note: 7.5-month is the mid-point between 3-month and 12-month, and 18-month is the mid-point between 12-month and 24-month. The exact mid-point will be determined as the day which has equal distance from two adjacent visits if there are odd number of days in between, or it is the earlier visit pluses a half number of days if there are event number of days in between,

If multiple readings are recorded within a single analysis-defined visit window, the following rules will apply:

- If there are 2 or more valid, non-missing observations within the same visit window, then the non-missing one closest to the scheduled visit day will be used in the analysis.
- If 2 valid observations are equidistant from the scheduled visit, then the non-missing observation with the earlier collection date will be used in the analysis.

Confidential Page 17 of 40

• If 2 or more valid observations are collected on the same day, then the non-missing observation with the earlier collection time will be included in the analysis.

If a visit window does not contain any observations, then the data will remain missing.

1.6.5 Missing Data Handling Rules

The primary approach to handling missing ranks for the primary and the key secondary endpoints will be multiple imputation. The details are provided in Section 2.2.1.3.

No imputation will be made for other secondary or exploratory endpoints. No imputation will be made for any safety or lab measurements.

1.7 MULTIPLE COMPARISONS/MULTIPLICITY

This trial has one primary and one key secondary endpoint. The study is comparing each of two doses to placebo; a hierarchically ordered testing procedure will be used to test the primary endpoint, then secondary endpoint for the high dose first, then for the lower dose. Nutrinia believe that insulin as a growth factor will have effect with both doses. We expect that there is an opportunity for exploring higher dose that may yield a more favorable clinical effect than the lower dose that was used in the phase 2. Thus for that reason, a hierarchal approach is now being considered in the analysis. This procedure will preserve the type 1 error rate of 5% overall. The detailed testing procedure and the stopping rules are described below.

- 1. The NTRA $-2112\ 2000\ \mu\text{IU}$ Insulin/ml group is compared with the placebo group for the primary endpoint using a two-sided test at the 0.05 significance level.
 - If the null hypothesis is not rejected, no further comparisons are made.
 - If the null hypothesis is rejected, comparisons continue in the next step.
- 2. The NTRA $-2112\ 2000\ \mu\text{IU}$ Insulin/ml group is compared with the placebo group for the key secondary endpoint using a two-sided test at the 0.05 significance level.
 - If the null hypothesis is not rejected, no further comparisons are made.
 - If the null hypothesis is rejected, comparisons continue in the next step.
- 3. The NTRA $-2112\ 400\ \mu\text{IU}$ Insulin/ml group is compared with the placebo group for the primary endpoint using a two-sided test at the 0.05 significance level.
 - If the null hypothesis is not rejected, the final comparison will not be made.
 - If the null hypothesis is rejected, the final comparison in the next step will be made.
- 4. The NTRA $-2112\ 400\ \mu\text{IU}$ Insulin/ml group is compared with the placebo group for the key secondary endpoint using a two-sided test at the 0.05 significance level.

Confidential Page 18 of 40

1.8 EXAMINATION OF SUBGROUPS

Descriptive statistics of effect sizes of treatment on the primary and key secondary endpoints will described in the following subgroups:

Statistical Analysis Plan V1.3

SAP Date: 06APR2018

- Gestation age group
- Region (North America, Europe, and Israel)
- Birth weight (< 750g, $\ge 750g$ and < 1000g, $\ge 1000g$ and < 1500g, $\ge 1500g$)
- Gender
- Ethnicity
- Enteral feedings type:
 - o Only own mother's milk
 - Only donor breast milk
 - Only human milk (combined)
 - o Only Infant formula
 - o Only own mother's milk and formula, in any combination of proportions
 - o Only donor breast milk and formula, in any combination of proportions
 - o Only human milk and infant formula, in any combination of proportions

For an infant to be in one of the above 7 categories, for example "Only own mother's milk", the infant had to be on own mother's milk for enteral feeding every day during the treatment period up to Day 28.

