12.4.8. Analyses of Predictor Variables

Effect of covariates: The effect on the primary and key secondary outcomes of the following variables will be assessed:

- GA
- Birth weight

- Gender
- Ethnicity
- Enteral feedings type
 - 1. Own mother's milk only to full enteral feeding
 - 2. Donor breast milk only to full enteral feeding
 - 3. Infant formula only to full enteral feeding
 - 4. Own mother's milk and formula, in any combination of proportions, to full enteral feeding
 - Donor breast milk and formula, in any combination of proportions, to full enteral feeding The methodology will be described in the SAP.

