1.2 STUDY ENDPOINTS

1.2.1 Primary Efficacy Endpoint

Numbers of days to achieve full enteral feeding (NFE) is defined as: Number of Days to the first day of achieving enteral feeding of at least 150 ml/kg/day, which must be sustained for at least 3 consecutive days.

For subjects who are marked as fluid restricted, the cut-off value for reaching FEF is 10% less, thus 135 mL/kg/day.

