1.2.2 Secondary Efficacy Endpoints

1.2.2.1 Key secondary endpoint:

Number of days to achieve discharge from hospital or readiness for discharge, whichever occurs first.

Readiness for discharge from hospital is defined as achieving all of the below:

- Infant weight ≥ 1800 g
- Stable body temperature
- Capable of oral feeding (reached full enteral feeding and not dependent on PN)

Note: enteral feeding may also include tube feeds.

Confidential Page 10 of 40

1.2.2.2 Other secondary endpoints:

• Growth velocity (g/kg/day) at 6, 8, and 10 days, the last day of treatment (or Day 28), day of discharge, 3-month corrected follow-up, 12-month corrected follow-up, and 24-month corrected follow up

- Change in Z-score at 6, 8 and 10 days, the last day of treatment (or Day 28), day of discharge, 3-month corrected follow-up, 12-month corrected follow-up, and 24-month corrected follow up from initiation of treatment
- Gain in body weight at 6, 8, and 10 days, the last day of treatment (or Day 28), day of discharge, 3-month corrected follow-up, 12-month corrected follow-up, and 24-month corrected follow up
- Number and percentage of infants reaching full enteral feeding within 6, 8, and 10 days from initiation of treatment.
- Total number of days receiving parenteral nutrition
- Number of days to 120Kcal/kg/day
- Number of days to wean-off PN

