1.3 SUMMARY OF THE STUDY DESIGN

1.3.1 General Study Design and Plan

[figure not shown]
The study is a multi-center, double-blind, randomized, three-arm, parallel-group, placebo-controlled study to assess the efficacy and safety of NTRA-2112.

Infants will be enrolled within 5 days from birth (at least 6 hours post birth and up to 120 hours post birth) and will be treated for 28 days or until hospital discharge (whichever comes first). The study also includes a follow-up period up to 24 months corrected age.

Full enteral feeding is defined as reaching 3 consecutive days in which the infant consumed at least 150 ml/kg/day of enteral nutrition.

Enrolled infants will be under supervision at a NICU.

[figure not shown]
Figure 1: Study Flow Diagram

Confidential Page 12 of 40

Statistical Analysis Plan V1.3 SAP Date: 06APR2018

Protocol No: FIT-04 Protocol Version: 7.0

Confidential Page 13 of 40

Statistical Analysis Plan V1.3 SAP Date: 06APR2018

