2.1.9 Breast Feeding

The volume of mother's milk (ml), total enteral feed, and percentage of mother's milk will be summarized using descriptive statistics by age day for the screening visit.

A subject data listing of breast feeding until treatment initiation will be provided on FAS.

Statistical Analysis Plan V1.3

SAP Date: 06APR2018

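### Feeding-type subgroups in SAP 1.8 are defined by milk received after randomisation, up to Day 28 or discharge, so the descriptive treatment effects by feeding type can be biased

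*SAP*

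**What the plan says.** SAP 1.8 plans "Descriptive statistics of effect sizes of treatment on the primary and key secondary endpoints" by several subgroups, one of which is enteral feeding type in seven categories. The membership rule is given by example: to count as fed only own mother's milk, an infant must have received it "every day during the treatment period up to Day 28". Under SAP 1.3.1 treatment lasts 28 days or until discharge if that is sooner, so the window closes at whichever comes first.

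SAP 1.2.1 defines the primary endpoint, NFE, as "Number of Days to the first day of achieving enteral feeding of at least 150 ml/kg/day", sustained for at least 3 consecutive days. The key secondary endpoint, NRD (SAP 1.2.2.1), is days to discharge or readiness for discharge. Readiness itself requires full enteral feeding.

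Protocol 12.4.8 used a different window, for example "Donor breast milk only to full enteral feeding". SAP Section 4 does not list the change. SAP 2.2.4 repeats the seven categories for the predictor analysis without stating any window.

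On feeding before treatment, SAP 2.1.9 summarises mother's-milk volume, total enteral feed and percentage of mother's milk at screening, and adds: "A subject data listing of breast feeding until treatment initiation will be provided on FAS".

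**The concern.** A subgroup contrast keeps the protection of randomisation only if membership is settled before treatment can influence it. Gestational age, region, birth weight, gender and ethnicity, the other factors in SAP 1.8, all meet that condition. Feeding type as defined does not. An infant fed only mother's milk through full feeding on Day 7 who receives a different milk on Day 20 changes category after the primary outcome has been recorded. An infant discharged before Day 28 has fewer days on which to break the rule, and discharge is part of the key secondary endpoint.

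If treatment changes feeding speed, discharge or the milk given, the infants in the same category on drug and on placebo need not be comparable. Readers are likely to look at this table closely, because the protocol's background says that insulin is present in mother's milk, loses its activity in pasteurised milk and is absent from formula.

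**Working it through.** **Planning figures.** SAP 1.3.3 gives mean NFE of 8.0 days (placebo) and 6.6 days (active), SD 3.5, two-sided 5% and 85% power. The normal approximation gives n = 2 × (1.960 + 1.036)² × (3.5/1.4)² = 112.2, so 113 per group. The exact t-test gives 113.2, so 114. The SAP states 115, which is reproduced to within 2 infants. The SAP gives no figure for the feeding-type subgroups.

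**Timing.** Planned mean NFE is 6.6 to 8.0 days and the window runs to Day 28 or discharge. For most infants, most of the window lies after the primary outcome.

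**Can the rule distort a contrast?** The documents give no rate of milk switching and no distribution of discharge before Day 28, so these inputs are assumptions:

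- NFE is gamma-distributed with the SAP means and SD, in whole days.
- Discharge day is 14 + 1.5 × NFE + normal noise (SD 8), and not before NFE + 3.
- Window length L = min(28, discharge day).
- The chance of staying in the category is (1 − p)^L, where p is the daily chance of another milk.
- Where slow feeders switch more, p is multiplied by exp(g × (NFE − 8)).
- There are 1,000,000 infants per arm. Differences are active minus placebo, in days.

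| Scenario | NFE difference in subgroup | NFE difference, all infants |
|---|---|---|
| No treatment effect on anything, p = 5% | 0.00 | 0.00 |
| Treatment shortens NFE; early discharge is the only link; p = 2–10% | −1.41 to −1.45 | about −1.40 |
| As above, but nobody discharged before Day 28, p = 5% | −1.39 | −1.40 |
| Treatment shortens NFE; slow feeders switch more (g = 0.1–0.2, p = 2–5%) | −1.03 to −1.21 | about −1.40 |
| Same with g = 0.2, p = 5%, nobody discharged before Day 28 | −1.04 | −1.40 |
| No true NFE effect; treatment lowers switching by 25–50% | +0.28 to +0.67 | 0.00 |
| Grouping independent of treatment and outcome | −1.39 | −1.40 |

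- Early discharge alone moves the NFE contrast by at most about 0.06 day. For NRD it gives −2.22 to −2.43 against about −2.1, a shift of 0.1 to 0.4 day.
- If slow feeders switch more, the NFE effect is understated by 14% ((1.41 − 1.21)/1.41) to 26% ((1.39 − 1.03)/1.39). NRD becomes −1.32 to −1.71 against about −2.1.
- If treatment reduces switching, a drug with no effect on NFE appears to delay feeding.

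**The protocol's window.** Under a window ending at full enteral feeding, with p = 5% and gamma scale 3.5²/8.0 = 1.531, the mean NFE of placebo members is 8.0/(1 − ln(0.95) × 1.531) = 8.0/1.0785 = 7.42 days. Under the SAP window the simulation gives 7.48. Both fall below the arm mean of 8.00, so selection on the outcome is present under either rule.

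**The case against.** The strongest reply is that these tables are descriptive. SAP 1.8 plans no subgroup or interaction test, and feeding type is outside the hierarchy in SAP 1.7. Milk given during dosing is also the relevant background exposure for a drug mixed into feeds for up to 28 days, whereas milk before first dose is early milk. Both points stand. The first limits the consequence, and the second is a real cost of the fix.

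A reader might also infer four stronger things that the documents do not support:

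- *That the subgroup effects are biased.* The text supports only that they can be. With no treatment effect on feeding, discharge or milk type, the contrast is unbiased. SAP 2.2.1.3.2 says discharge can take much longer than 28 days, and infants still in hospital at Day 28 all have the same window length.
- *That infants with NEC or who die are more likely to stay in a single-milk category because they have fewer days at risk.* Both documents end treatment at Day 28 or discharge, and the protocol describes NEC as stopping enteral feeds. Read literally, a day without feeds fails the every-day rule, so such an infant may fit no category. The SAP does not say.
- *That chances of staying in one category measure the bias.* At an assumed 2–5% daily switch, 12 days against 28 gives 0.98^12 = 0.78 against 0.98^28 = 0.57, and 0.95^12 = 0.54 against 0.95^28 = 0.24, ratios of 1.4 and 2.3. These compare two hypothetical infants, not two arms.
- *That the protocol's window was sound and the SAP spoiled it.* The protocol's window is also post-randomisation, and its length is the primary outcome itself.

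**Conclusion.** The point holds in a limited form. The SAP 1.8 rule conditions on feeding after randomisation, mostly after the primary outcome and, for infants discharged before Day 28, over a window tied to the key secondary endpoint. Effect sizes by feeding type can therefore be biased if treatment affects feeding, discharge or milk type. Sign and size depend on switching and discharge patterns that the documents do not give, so the simulated errors (zero to several tenths of a day in NFE, in either direction) are illustrations and not estimates for this trial. The primary and key secondary tests, alpha and the sample size are untouched. This is a minor improvement to a descriptive analysis.

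**What to change.** In SAP 1.8 and 2.2.4:

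1. Report treatment effects by feeding type using milk received before first dose. SAP 2.1.9 supports three groups: own mother's milk only (100% of enteral feed), mixed, and none (0%). Split donor milk from formula only if that was recorded before dosing; SAP 2.1.9 does not show that it was.
2. Keep the seven Day-28 categories as a description of exposure, labelled as post-randomisation and not causal.
3. State how days without enteral feeds are classed, so that an infant whose feeds were interrupted has a defined place.
4. Note in SAP Section 4 that the feeding-type definition differs from protocol 12.4.8. Returning to the protocol's window would not solve the problem.

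The cost is SAP wording and some table programming, with no change to tests, alpha or sample size. The downside is that early milk may differ from the milk given during most of the dosing period, so the pre-dose groups answer a somewhat different question. The Day-28 exposure tables remain for readers who want that description.

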1.9 POOLING OF CENTERS

The study centers are not planned to be used as a stratification factor nor a covariate in the statistical modeling and testing, therefore it is not necessary to pool small centers together.

2 STATISTICAL ANALYSES

Although the study includes follow-up visits up to 24 months corrected age, the primary analysis will be completed after the last subject has completed the 3 month corrected age follow-up visit. At that time, all data up to and including the 3 month follow-up visit will be cleaned and the study unblinded.

Subject Information

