11.2. Causality

The Investigator will determine the relationship of an AE to the study drug and will record it on the source documents and eCRF, using the categories defined below.

Causality Category	Description		
Unlikely	A clinical event, including a laboratory test abnormality, with a temporal relationship to drug administration, that makes a causal relationship improbable, and in which other drugs, chemicals, or the underlying disease provide plausible explanations. For the purpose of this protocol, the term unlikely will be considered not related to study medication and will be termed an "Adverse Event".		
Possible	A clinical event, including a laboratory test abnormality, with a reasonable time sequence to administration of the drug, but that could also be explained by concurrent disease or other drugs or chemicals. Information on drug withdrawal may be lacking or unclear. For the purpose of this protocol, an event that has possible relationship to study medication will be defined as a "Suspected Adverse Drug Reaction".		

Probable	A clinical event, including a laboratory test abnormality, with a reasonable time sequence to administration of the drug, unlikely to be attributed to concurrent disease or other drugs or chemicals, and that follows a clinically reasonable response on withdrawal. For the purpose of this protocol, an event that has probable relationship to study medication will be defined as an "Adverse Drug Reaction".
----------	--

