1.2.5 Other Endpoints

The first three items below are measured at 24 months corrected follow-up only, the last two items are assessed at 12-month corrected follow-up and 24-month corrected follow-up.

- Bayley scale of infant and toddler development
- Neurodevelopment disability composite
- Child behavior checklist total problem score
- Observer reported outcomes
- Co-morbidities related to Pre-maturity

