2.2.1.6 Sensitivity Analysis: The Per Protocol Set

Per protocol set consists of subjects in FAS who do not have any important protocol deviations. The important protocol deviations will be determined before the database is unblinded. The analysis of the primary and the key secondary endpoint will be repeated on the per protocol set.

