2.3.2.1 Adverse Events

Adverse events (AEs) experienced by the subjects will be collected from initiation of dosing through the final study visit and will be coded using the latest version of the Medical Dictionary for Regulatory Activities (MedDRA) per the Data Management Plan.

Adverse event data will be categorized according to their onset date into the following study periods:

• Treatment-emergent adverse events are the ones that they started during or after administration of the first dose of study medication up till the last dose date + 30 days. In addition, medical history events that worsen in severity after the start of dosing will be considered treatment-emergent adverse events.

Confidential Page 30 of 40

AEs during the 3 month corrected age follow up period : < last dose date + 30 days -
 Month 3 follow-up visit

- AEs during the 12 month corrected age follow up period : < Month 3 follow-up visit <= Month 12 follow-up visit
- AEs during the 24 month corrected age follow up period : < Month 12 follow-up visit <= Month 24 follow-up visit

If an AE has a missing onset date then unless the stop date of the AE indicates otherwise, this will be considered an ongoing AE. Similarly, if an AE has a partial onset date, then unless the partial onset date or the stop date indicates otherwise, this will be considered an ongoing AE.

Only those AEs that are treatment-emergent will be included in summary tables. All AEs, treatment-emergent or otherwise, will be presented in subject data listings.

TEAEs will be summarized by treatment group, separately for the four reporting periods above. The incidence of TEAEs will be reported as the number (percent) of subjects with TEAEs within SOC and PT. Subjects will be counted only once within a SOC and PT, even if the subject experienced more than one TEAE within a specific SOC and PT. The number (percent) of subjects with TEAEs will also be summarized by maximum severity of Common Terminology Criteria for Adverse Events (CTCAE) and the relationship to the study drug (unlikely, possible, probable).

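### The SAP unblinds the study at the 3-month cut without limiting who learns the allocation, although adverse events and rated outcomes continue to 24 months

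*SAP*

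**What the plan says.** SAP section 2 sets the timing: "the primary analysis will be completed after the last subject has completed the 3 month corrected age follow-up visit". It then states: "At that time, all data up to and including the 3 month follow-up visit will be cleaned and the study unblinded". No role is named as receiving the allocation or as staying blinded.

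Follow-up does not end there. SAP 1.6.3 puts the end of study at the 24-month corrected-age visit. Still to be collected after the cut, for infants who have not yet reached those visits:

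- **Adverse events.** Under SAP 2.3.2.1 they "will be collected from initiation of dosing through the final study visit", with separate 12- and 24-month periods; "TEAEs will be summarized by treatment group, separately for the four reporting periods above". On causality, Protocol 11.2 says: "The Investigator will determine the relationship of an AE to the study drug".
- **Developmental and rated outcomes.** SAP 1.2.5 lists the Bayley scale, a neurodevelopment disability composite, the child behavior checklist, observer reported outcomes and co-morbidities. Of these, "The first three items below are measured at 24 months corrected follow-up only"; the other two are assessed at 12 and 24 months.
- **Growth.** SAP 2.2.2 gives ANCOVA estimates and P-values for weight-based measures at 12 and 24 months, labelled exploratory.

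**The concern.** The trial is described as double-blind with follow-up to 24 months corrected age, yet one sentence in the SAP opens the study while judgement-dependent data are still being collected. Relatedness calls, event coding and rated outcomes can all shift, even unintentionally, once the arm is known. For these data, masking is the main protection for the comparison between arms, and it cannot be restored once lost.

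Protocol 15.6 accepts that long-term effects on insulin antibodies, or on the prevention of diabetes, cannot be excluded. The 12- and 24-month data are the trial's own evidence on such effects.

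**Working it through.** The SAP gives no figure to reproduce here. The check sets the sections side by side and then estimates how many visits could be affected.

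**1. Who may be unblinded.** SAP section 2 speaks of the study being unblinded. SAP 2.2.1.6 is narrower: "The important protocol deviations will be determined before the database is unblinded". Neither names roles. The blinding text in SAP 1.3.2 covers emergency unblinding only. Elsewhere the documents do name roles: Protocol 12.4.12 keeps the sponsor blinded at the futility look, SAP 3.1 gives the sample size re-estimation to a blinded statistician, and Protocol 9.5.2 keeps the Medical Monitor blinded to cumulative data throughout. An unrestricted unblinding at 3 months is hard to square with that last rule.

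**2. Would sponsor-only unblinding be enough?** Not by itself. Protocol 11.4 has the sponsor review every investigator assessment of an adverse event and determine its seriousness and its relationship to study medication. Protocol 11.3 has the sponsor or its designee assign the MedDRA terms. Unless there is a firewall inside the sponsor, later relatedness and coding decisions could be made with the arm known.

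**3. Does relatedness affect which data exist?** Yes. Under Protocol 9.5.1, a withdrawal after day 28 caused by an event judged not product-related ends follow-up. Under Protocol 11.3, related events and all serious events are followed to resolution. An unmasked relatedness call could therefore change what is collected, not only how it is labelled.

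**4. How many visits fall after the cut.** For each infant the 24-month visit comes 24 − 3 = 21 months after the 3-month visit, and the 12-month visit 12 − 3 = 9 months after it. Assume uniform accrual over T months (the documents give no accrual period), similar gestational age at entry, and unblinding at the last infant's 3-month visit. An infant enrolled at time u has its 24-month visit after the cut if u + 21 > T, so

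- share of 24-month visits after the cut = min(1, 21/T)
- share of 12-month visits after the cut = min(1, 9/T)

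Applied to the SAP 1.3.3 total of 390 infants (130 per group), assuming all are followed up:

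| T (months) | 24-month visits after cut | 12-month visits after cut |
|---|---|---|
| 12 | 100% (390) | 75% (about 292) |
| 24 | 87.5% (about 341) | 37.5% (about 146) |
| 36 | 58% (about 228) | 25% (about 98) |
| 48 | 44% (about 171) | 19% (about 73) |

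Time spent on data cleaning before unblinding would lower these shares. With a lag of L months the 24-month share becomes min(1, (21 − L)/T).

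**The case against.** The strongest reply is that bias arises only if someone who rates or classifies an outcome learns the allocation, and the SAP does not say that anyone in that position will. The sentence stands in the statistical section beside data cleaning and analysis timing, and SAP 2.2.1.6 speaks of the database being unblinded. Both fit release to an analysis team.

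A reader might infer that the plan releases allocations to families and sites. The documents do not say so. Nor can it be said that no safeguard exists: Protocol 9.1 to 9.4 and the body of SAP 2.4, the section on the developmental and observer reported outcomes, are not readable in the public text. A reader might also describe these outcomes as parent-reported, but the readable text does not say who completes the checklist or the observer reports.

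The consequences are limited too. Protocol 12.4.7 makes the 12- and 24-month data descriptive, SAP 2.2.2 calls its growth tests exploratory, and none of these outcomes is in the testing hierarchy of SAP 1.7. For adverse events, SAP 2.3.2.1 restricts summary tables to treatment-emergent events, defined as up to 30 days after the last dose, yet also promises summaries for four periods reaching 24 months. How far late relatedness calls enter the tabulated comparison is therefore unclear.

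All of this stands, and it limits how strongly the point can be put. It does not remove the point: the wording sets no limit, and the narrower reading still reaches the sponsor staff who determine relatedness and assign codes.

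**Conclusion.** The wording of SAP section 2 permits sites, assessors and sponsor safety reviewers to know the arm at assessments made after the 3-month cut, and it is in tension with the Medical Monitor's continued blinding in Protocol 9.5.2. It should be restricted, or should cite the safeguard if one exists in the unreadable sections.

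The risk is confined to long-term safety, growth and developmental comparisons, which are descriptive or exploratory. The primary endpoint, a feeding outcome within the 28-day treatment period, is complete before the cut. Infants whose later visits precede the cut are assessed before any unblinding. Under the accrual assumptions above, roughly 44% to 100% of 24-month visits and 19% to 75% of 12-month visits would follow it.

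A reader might go further and conclude that the long-term comparison will be biased or is unusable. The documents do not support that: exposure is permitted, not stated, and the size of any bias cannot be estimated from them.

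**What to change.** Replace the unblinding sentence in SAP section 2 with wording such as:

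> Only the team performing the 3-month analysis will be unblinded. Families, site staff, developmental assessors, the Medical Monitor and anyone coding or assessing adverse events remain blinded, and individual allocations are not released, until the 24-month database lock (emergency unblinding and DMC access excepted).

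If an equivalent safeguard already exists in Protocol section 9 or SAP 2.4, cite it at this point. The change must be in place before the 3-month unblinding.

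The text change is small. The practical cost is an access firewall within the sponsor, separating the analysis team from those who review relatedness and assign codes, for about 21 months (from the last infant's 3-month visit to the 24-month visit). Whether existing staff can cover that separation cannot be judged from the documents.
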